10.1.2 STUDY CLOSURE

The sponsor may temporarily or permanently stop the study for any reason. If the study is prematurely terminated or suspended, the sponsor will notify clinical site investigators who must promptly inform their IEC/IRB and study participants. The sponsor will provide instructions for interim or closeout procedures.

10.1.3 CONFIDENTIALITY AND PRIVACY

The electronic enrollment log at each clinical site which links participant identifiers to their screening identification number will be treated as confidential and filed by the investigator in the study file. To ensure participant confidentiality, no copy will be made. All reports and communications relating to the study will identify participants by identification number.

Privacy of Personal Data

The collection and processing of personal data from participants enrolled in this study will be limited to those data that are necessary to fulfill the objectives of the study. These data must be collected and processed with adequate precautions to ensure confidentiality and compliance with applicable data privacy protection laws and regulations. Appropriate technical and organizational measures to protect the personal data against unauthorized disclosures or access, accidental or unlawful destruction, or accidental loss or alteration must be put in place. Sponsor personnel whose responsibilities require access to personal data agree to keep the identity of participants confidential. The informed consent obtained from the participant (or his or her LAR) includes explicit consent for the processing of personal data and for the investigator/institution to allow direct access to his or her original medical records (source data/documents) for study-related monitoring, audit, IEC/IRB review, and regulatory inspection. This consent also addresses the transfer of the data to other study-related entities and to other countries.

The participant has the right to request through the investigator access to his or her personal data and the right to request rectification of any data that are not correct or complete. Reasonable steps will be taken to respond to such a request, taking into consideration the nature of the request, the conditions of the study, and the applicable laws and regulations.

10.1.4 FUTURE USE OF STORED SPECIMENS AND DATA

Plasma, serum and samples for DNA extraction will be processed and stored at the clinical sites for batch shipping to the study biobank, consistent with local regulatory requirements. The site investigator will maintain full traceability of collected biological sample shipment or disposal (where appropriate) and documentation of receipt of arrival. The sample receiver keeps full traceability of samples arrival, storage and use until used or disposed of or until further shipment.

Withdrawal of informed consent for biological samples

If a patient withdraws consent for the use of biological samples, the samples will be disposed of/destroyed, and the action documented. If samples are already analyzed, the sponsor is not obliged to

destroy the results of this research. When the site investigator receives notification of withdrawal of consent to the use of collected biological samples, he/she should:

- document this notification in the participant's record
- Ensure that biological samples from that participant, if stored at the study site, are immediately identified, disposed of/destroyed, and the action documented
- If the participant's samples have been shipped to the study biobank, ensure the laboratory(ies) holding the samples is/are informed about the withdrawn consent immediately and that samples are disposed of/destroyed, the action documented and the signed documentation returned to the study site for archiving
- Ensures that the participant and sponsor are informed of the sample disposal.

For additional information on participant discontinuation or withdrawal, see [Section 7 STUDY INTERVENTION DISCONTINUATION AND PARTICIPANT DISCONTINUATION/WITHDRAWAL](#).

10.1.5 TRIAL COMMITTEES

Executive Committee

The Executive Committee (EC) consists of members of the academic leadership of the study and the sponsor. Ad hoc members may be appointed as necessary. The EC has overall responsibility for the design, conduct and reporting of the study. The EC will monitor overall safety during the study and will receive any recommendations from the DSMC regarding possible additional analyses or modifications to the study and decide whether to accept them. The EC will oversee the implementation of any modifications to the study and publication of the results.

Clinical Endpoint Committee

A CEC, comprised of physicians blinded to treatment assignment, will review source documentation and centrally adjudicate clinical and functional outcomes for the trial. The CEC will be responsible for adjudicator training, endpoint definitions and classification procedures for suspected thrombotic events and quality control procedures as described in the CEC charter.

Data Safety Monitoring Committee

A DSMC will be appointed by and provide its input to the EC to monitor safety and evidence of effectiveness and to recommend modifications to the adaptive trial design. Modifications to eligibility criteria could include enrollment in Phase 3 of participants 16-17 years of age, based on safety data with weight-based dosing of rNAPc2 in the target population. For safety, ISTH major bleeding, SAEs and all-cause mortality will be monitored monthly by the DSMC Chairperson and at scheduled interim analyses by the full committee (Section 9.4.6 Planned Interim Analyses). Based on monthly reviews, the DSMC Chairperson may call additional unscheduled meetings at anytime during the study. In addition, the study team may advise the DSMC chair of severe safety events (e.g. fatal bleeding) in a blinded fashion in real time, enabling the chair to work with the DSMC statistician and committee as needed to ensure the safety of study participants. The DSMC will operate under the rules of a charter that will be reviewed at the organizational meeting of the DSMC and approved by the principal investigator and Sponsor.

10.1.6 SAFETY OVERSIGHT

A DSMC will be appointed by and provide its input to the EC to monitor safety and evidence of effectiveness and to recommend modifications to the trial design.

10.1.7 CLINICAL MONITORING

The Sponsor or designee will review eCRF data for accuracy and completeness via centralized, remote, and/or on-site monitoring methods described in the Monitoring Plan. Representatives of the sponsor may visit the study site at any time during or after completion of the study to conduct an audit of the study in compliance with regulatory guidelines and company policy. These audits will require access to all study records, including source documents, for inspection. Participant privacy must, however, be respected. The investigator and study-site personnel are responsible for being present and available for consultation during routinely scheduled study-site audit visits conducted by the sponsor or its designees. Similar auditing procedures may also be conducted by agents of any regulatory body, either as part of a national GCP compliance program or to review the results of this study in support of a regulatory submission. The investigator should immediately notify the sponsor if he or she has been contacted by a regulatory agency concerning an upcoming inspection.

10.1.8 QUALITY ASSURANCE AND QUALITY CONTROL

Steps to be taken to ensure the accuracy and reliability of data include the selection of qualified investigators and appropriate study sites and review of protocol procedures with the investigator and study-site personnel before the study. Guidelines for eCRF completion will be provided and reviewed with participating study-site personnel before the start of the study. The Sponsor, or designee will review eCRF data for accuracy and completeness via centralized, remote, and/or on-site monitoring methods; any discrepancies will be resolved with the investigator or designee, as appropriate.

10.1.9 DATA HANDLING AND RECORD KEEPING

10.1.9.1 DATA COLLECTION AND MANAGEMENT RESPONSIBILITIES

Study data will be recorded into the electronic data capture system. The data system includes password protection and internal quality checks to identify data that appear inconsistent, incomplete, or inaccurate. Clinical data will be entered directly from source documents.

10.1.9.2 STUDY RECORDS RETENTION

In compliance with the ICH/GCP guidelines, the investigator/institution will maintain all CRF and all source documents that support the data collected from each participant, as well as all study documents as specified in ICH/GCP Section 8, Essential Documents for the Conduct of a Clinical Trial, and all study documents as specified by the applicable regulatory requirement(s). The investigator/institution will take measures to prevent accidental or premature destruction of these documents.

Essential documents must be retained until at least two (2) years after the last approval of a marketing application in an ICH region and until there are no pending or contemplated marketing applications in an ICH region or until at least two (2) years have elapsed since the formal discontinuation of clinical

development of the investigational product. These documents will be retained for a longer period if required by the applicable regulatory requirements or by an agreement with the sponsor. It is the responsibility of the sponsor to inform the investigator/institution as to when these documents no longer need to be retained.

If the responsible investigator retires, relocates, or for other reasons withdraws from the responsibility of keeping the study records, custody must be transferred to a person who will accept the responsibility. The sponsor must be notified in writing of the name and address of the new custodian. Under no circumstance shall the investigator relocate or dispose of any study documents before having obtained written approval from the sponsor. If it becomes necessary for the sponsor or the appropriate regulatory authority to review any documentation relating to this study, the investigator/institution must permit access to such reports.

10.1.10 PROTOCOL DEVIATIONS

Protocol deviations will be identified manually and programmatically prior to unblinding. However, as the primary analysis is ITT, protocol deviations will not imply exclusion from analysis. A summary of major protocol deviations will be given by frequency tables showing the number of participants with major protocol deviations overall and by deviation.

10.1.11 PUBLICATION AND DATA SHARING POLICY

All information, including but not limited to information regarding rNAPc2 or the sponsor's operations (e.g., patent application, formulas, manufacturing processes, basic scientific data, prior clinical data, formulation information) supplied by the sponsor to the investigator and not previously published, and any data, including research data, generated as a result of this study, are considered confidential and remain the sole property of the sponsor. The investigator agrees to maintain this information in confidence and use this information only to accomplish this study and will not use it for other purposes without the sponsor's prior written consent.

The investigator understands that the information developed in the study will be used by the sponsor in connection with the continued development of rNAPc2, and thus may be disclosed as required to other clinical investigators or regulatory agencies. To permit the information derived from the clinical studies to be used, the investigator is obligated to provide the sponsor with all data obtained in the study. The results of the study will be reported in a Clinical Study Report generated by the sponsor and will contain data from all study sites that participated in the study as per protocol. Study participant identifiers will not be used in publication of results. Any work created in connection with performance of the study and contained in the data that can benefit from copyright protection (except any publication by the investigator as provided for below) shall be the property of the sponsor as author and owner of copyright in such work.

Consistent with Good Publication Practices and International Committee of Medical Journal Editors (ICMJE) guidelines, the sponsor shall have the right to publish such primary (multicenter) data and information without approval from the investigator. The investigator has the right to publish study-site-specific data after the primary data are published. If an investigator wishes to publish information from the study, a copy of the manuscript must be provided to the sponsor for review at least 60 days before submission for publication or presentation. Expedited reviews will be arranged for abstracts, poster presentations, or other materials. If requested by the sponsor in writing, the investigator will withhold such publication for up to an additional 60 days to allow for filing of a patent application. In the event

that issues arise regarding scientific integrity or regulatory compliance, the sponsor will review these issues with the investigator. The sponsor will not mandate modifications to scientific content and does not have the right to suppress information.

For multicenter study designs and sub-study approaches, secondary results generally should not be published before the primary endpoints of a study have been published. Similarly, investigators will recognize the integrity of a multicenter study by not submitting for publication data derived from the individual study site until the combined results from the completed study have been submitted for publication, within 18 months after the study end date, or the sponsor confirms there will be no multicenter study publication. Authorship of publications resulting from this study will be based on the guidelines on authorship, such as those described in the ICMJE Recommendations for the Conduct, Reporting, Editing and Publication of Scholarly Work in Medical Journals, which state that the named authors must have made a significant contribution to the conception or design of the work; or the acquisition, analysis, or interpretation of the data for the work; and drafted the work or revised it critically for important intellectual content; and given final approval of the version to be published; and agreed to be accountable for all aspects of the work in ensuring that questions related to the accuracy or integrity of any part of the work are appropriately investigated and resolved.

10.1.12 CONFLICT OF INTEREST POLICY

The Sponsor will register and disclose the existence and results of clinical studies as required by law. The disclosure of the final study results will be performed after the end of study.

10.2 ACRONYMS

ACTT	Adaptive COVID-19 Treatment Trial
ADA	Anti-drug antibodies
AE	Adverse event
ALI	Acute limb ischemia
ALT	Alanine aminotransferase
ANCOVA	Analysis of covariance
AST	Aspartate aminotransferase
CEC	Clinical endpoint committee
CRA	Clinical Research Associate
DIC	Disseminated intravascular coagulation
DSMC	Data Safety Monitoring Committee
DNA	Deoxyribonucleic acid
DVT	Deep vein thrombosis
EC	Executive Committee
eCRF	Electronic case report form
eGFR	Estimated glomerular filtration rate
EMR	Electronic medical record
fVIIa	Activated factor VII
fXa	Activated factor X
GCP	Good Clinical Practice
HIPAA	Health Insurance Portability and Accountability Act
HITT	Heparin-induced thrombocytopenia and thrombosis

HR	Hazard ratio
HS	Healthy subjects
hsCRP	High sensitivity C reactive protein
HSV1	Herpes simplex virus 1
ICF	Informed consent form
IB	Investigator's Brochure
ICH	International Conference on Harmonisation
ICMJE	International Committee of Medical Journal Editors
IL-6	Interleukin-6
IND	Investigational New Drug Application
IEC/IRB	Independent Ethics Committee/Institutional Review Board
ISTH	International Society on Thrombosis and Haemostasis
ITT	Intention-To-Treat
IV	Intravenous
LAR	Legally authorized representative
LMWH	Low molecular weight heparin
MAD	Multiple ascending dose
mITT	Modified intention-to-treat
NSTE-ACS	Non-ST elevation acute coronary syndrome
PAR	Protease activated receptor
PCI	Percutaneous coronary intervention
PCR	Polymerase chain reaction
PCFS	Post COVID-19 Functional Status
PK	Pharmacokinetic
PT	Prothrombin time
PTT	Partial thromboplastin time
rfVIIa	Recombinant activated factor VII
rNAPc2	Recombinant nematode anticoagulant protein c2
SAD	Single ascending dose
SAE	Serious Adverse Event
SAP	Statistical Analysis Plan
SARS-CoV-2	Severe acute respiratory syndrome coronavirus 2
SC	Subcutaneous
SoA	Schedule of Activities
SoC	Standard of care
SUSAR	Suspected unexpected serious adverse reactions
TF	Tissue factor
UFH	Unfractionated heparin
ULN	Upper limit of normal
UP	Unanticipated Problem
VTE	Venous thromboembolic event
WBC	White blood cell count

10.3 HEPARIN GUIDANCE

Population	Guidance
VTE prophylaxis in non-ICU hospitalized COVID-19 patients	
 1. A universal strategy of routine thromboprophylaxis with standard-dose UFH or LMWH should be used after careful assessment of bleed risk, with LMWH as the preferred agent. Intermediate dose LMWH may also be considered. 2. VTE prophylaxis recommendations should be modified based on extremes of body weight, severe thrombocytopenia (i.e. platelet counts of $50\,000 \times 10^9$ per liter or $25\,000 \times 10^9$ per liter) or deteriorating renal function.
VTE prophylaxis in sick ICU hospitalized COVID-19 patients	
 1. Routine thromboprophylaxis with prophylactic-dose UFH or LMWH should be used after careful assessment of bleed risk. Intermediate-dose LMWH (50% of respondents) can also be considered in high risk patients. Patients with obesity as defined by actual body weight or BMI should be considered for a 50% increase in the dose of thromboprophylaxis. Treatment-dose heparin should not be considered for primary prevention until the results of randomized controlled trials are available. 2. Multi-modal thromboprophylaxis with mechanical methods (i.e. intermittent pneumatic compression devices) should be considered.

Perioperative and Critical Care Thrombosis and Haemostasis of the Scientific, Standardization Committee of the International Society on Thrombosis and Haemostasis.³⁰

10.4 POST-COVID FUNCTIONAL STATUS SCALE

The post-COVID-19 functional status (PCFS) scale³¹ focuses on relevant aspects of daily life during follow-up after the infection. The scale is intended to help users becoming aware of current functional limitations in COVID-19 patients, whether or not as a result of the specific infection, and to objectively determine this degree of disability. This will aid in demarcating effective and ineffective COVID-19 therapies on functional outcomes in an experimental setting, as well as pave the road for value-based healthcare.

General description of each scale grade

- Grade 0 reflects the absence of any functional limitation.
- Grades 1 and 2 correspond to a condition for which usual duties/activities could be carried out, defined as any activity that patients undertake on a monthly basis or more frequently, either at home or at work/study. Importantly, this includes sports and social activities. Specifically, *Grade 1* is reserved for patients with some symptoms, which however do not prohibit or limit doing any usual activities. Grade 2 is reserved for patients who are able to independently perform all usual activities

but at a lower intensity, sometimes combined with mild limitations in participation in usual social roles.

- Grade 3 accounts for moderate functional limitations that force patients to structurally modify usual activities, reflecting the inability to perform certain activities which, therefore, need to be taken over by others. Those patients may require assistance in instrumental activities of daily living, e.g. managing basic household chores, community mobility, shopping for groceries or necessities, or participation in usual social roles is restricted.
- Grade 4 describes those patients with severe functional limitations who require assistance with activities of daily living (ADL), not necessarily administered by a certified nurse. It should be indicated that assistance with some ADL activities, e.g. using the toilet, managing routine daily hygiene and functional mobility, is essential. Participation in usual social roles is likely restricted.

Timing

The PCFS is intended to be assessed 1) at the time of discharge from the hospital and 2) in the first weeks after discharge to monitor direct recovery. Providing a pre-COVID-19 reference value will allow to measure the change in status. To measure this pre-COVID-19 functional status, the functional status assessment should refer to the status 1 month prior to the infection. Assessment of the pre-COVID-19 functional status should be performed after assessment of the current functional status.

General Instructions

Characteristics of the PCFS scale

The scale is ordinal, has 6 steps ranging from 0 (no symptoms) to 5 (death, D), and covers the entire range of functional outcomes by focusing on limitations in usual duties/activities either at home or at work/study, as well as changes in lifestyle.

Procedure

The post-COVID-19 functional status scale can be assessed by either medical experts or trained interviewers during a short, structured interview. For any type of data collection, raters are encouraged to base their assessments on the *ability* of the patient to perform the activity rather than whether the patient actually performs the activity currently. This prevents overestimation of the severity of symptoms in patients who have chosen to abandon or who simply never performed certain activities.

Information should be ideally obtained primarily from the patient and/or a close friend or caregiver (proxy) who is familiar with the daily routine of the patient. If the patient lacks insight into some questions or if responses are inconsistent, it may be helpful to interview a caregiver or relative independently. Limitations or symptoms may vary over time, *the measurement concerns the average situation of the past week (except for when assessed at discharge, in that case it concerns the situation of the day of discharge)*. The standardized questions cover 5 sections corresponding to the separate levels of disability, see below table.. However, it is encouraged to ask questions beyond those stated to ensure that the patient has grasped the meaning of the question and to further clarify their responses. Additionally, it is recommended to adapt the interviewing strategy according to the patient's status and his/her answers. Open questions can be a great way to start the interview, during which some key information will be obtained useful to score the patients. Later, more targeted or even closed questions can help to make a clear distinction between adjacent grades. The corresponding PCFS scale grade is provided in the column besides each specific response. In case two grades seem to be appropriate, the

patient will be assigned to the highest grade with the most limitations.

Question	PCFS scale grade if the answer is 'YES'
1. SURVIVAL	
1.1 Has the patient died after the COVID-19 diagnosis?	D
2. CONSTANT CARE Explanation: meaning someone else needs to be available at all times. Care may be provided by either trained or an untrained caregiver. The patient will usually be bedridden and may be incontinent.	
2.1 Do you require constant care?	4
2. BASIC ACTIVITIES OF DAILY LIVING Explanation: assistance includes physical assistance, verbal instruction, or supervision by another person. It may be considered essential when there is a need for physical help (by another person) with an activity or for supervision, or the patient needs prompting or reminding to do a task. The need for supervision for safety reasons should be due to objective danger that is posed, rather than 'just in case'.	
3.1 Is assistance essential for eating? (Eating without assistance: food and implements may be provided by others)	4
3.2 Is assistance essential for using the toilet? (Using toilet without assistance: reach toilet/commode; undress sufficiently; clean self; dress and leave)	4
3.3 Is assistance essential for routine daily hygiene? (Routine hygiene includes only washing face, doing hair, cleaning teeth/fitting false teeth. Implements may be provided by others without considering this as assistance)	4
3.4 Is assistance essential for walking? (Walking without assistance: if absolutely necessary, able to walk indoors or around house or ward, may use any aid, however not requiring physical help or verbal instruction or supervision from another person)	4
4. INSTRUMENTAL ACTIVITIES OF DAILY LIVING Explanation: assistance includes physical assistance, verbal instruction, or supervision by another person. It may be considered essential when there is a need for physical help (by another person) with an activity or for supervision, or the patient needs prompting or reminding to do a task. The need for supervision for safety reasons should be due to objective danger that is posed, rather than 'just in case'.	
4.1 Is assistance essential for basic household chores which are important for daily life? (E.g. preparing a simple meal, doing the dishes, take out the garbage; exclude chores that do not need to be done every day)	4
4.2 Is assistance essential for local travel? (Local travel without assistance: the patient may drive or use public transport to get around. Ability to use a taxi is sufficient, provided the patient can manage to call and instruct the driver)	4
4.3 Is assistance essential for local shopping? (The patient is not able to buy groceries or necessities by him or herself)	3
5. PARTICIPATION IN USUAL SOCIAL ROLES Explanation: this section concerns impairment in fulfilment of major social roles (not social or financial circumstances).	
5.1 Is adjustment essential for duties/activities at home or at work/study because you are unable to perform these yourself (e.g. resulting in a change in the level of responsibility, a change from full-time to part-time work or a change in education)? (Work refers to both paid employment and voluntary work. Special arrangements which allow someone to return to work, even though normally he/she wouldn't be able to work, should be considered as adjustment of work.)	3
5.2 Do you occasionally need to avoid or reduce duties/activities at home or at work/study or do you need to spread these over time (while you are basically able to perform all those activities)?	2

5.3 Can you no longer take good care of loved ones as before? (Taking good care includes babysitting, looking after your partner, parents, grandchildren or dependent others.)	3
5.4 Since the COVID-19 diagnosis, have there been problems with relationships or have you become isolated? (These problems include communication problems, difficulties in relationships with people at home or at work/study, loss of friendships (increase in) isolation, etc.)	3
5.5 Are you restricted in participating in social and leisure activities? (Comprising hobbies and interests, including going to a restaurant, bar, cinema, going for walks, playing games, reading books, etc.)	2
6. SYMPTOM CHECKLIST Explanation: these can be any symptoms or problems reported by the patients or found on physical examination. Symptoms include but are not limited to: dyspnea, pain, fatigue, muscle weakness, memory loss, depression and anxiety.	
6.1 Do you report symptoms through which usual duties/activities need to be avoided, reduced or spread over time?	2
6.2 Do you report any symptoms, resulting from COVID-19, without experiencing functional limitations?	1
6.3 Do you have problems with relaxing or do you experience COVID-19 as a trauma? ('Trauma' is defined as: suffering from intrusive memories, flashbacks or avoidance responses, associated with having experienced COVID-19.)	1

Assigning a grade on the post-COVID-19 functional status scale

The overall rating is simply the poorest functional status indicated by the patient's answers (the highest grade corresponds with the most limitations). If a respondent has no limitations or symptoms, then the appropriate scale grade is 0.

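### Protocol Section 10.4 contradicts itself on PCFS scoring: needing help with household chores or local travel is Grade 3 in the grade descriptions but scores 4 in the interview table

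*Protocol*

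**What the plan says.** Protocol Section 8.2 uses the PCFS at hospital discharge and at 30 days for patients who have been discharged, and sends sites to Section 10.4 for instructions. Section 10.4 has three parts that bear on scoring.

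- **Grade descriptions.** On severity: "Grade 3 accounts for moderate functional limitations that force patients to structurally modify usual activities". On content: "Those patients may require assistance in instrumental activities of daily living, e.g. managing basic household chores, community mobility, shopping for groceries or necessities". Grade 4 is the severe level, where "assistance with some ADL activities, e.g. using the toilet, managing routine daily hygiene and functional mobility, is essential".
- **Interview table.** Under the heading "4. INSTRUMENTAL ACTIVITIES OF DAILY LIVING" there are three items. Item 4.1 ("Is assistance essential for basic household chores which are important for daily life") carries grade 4. Item 4.2 ("Is assistance essential for local travel") carries grade 4. Item 4.3, on local shopping, carries grade 3.
- **Rule for the overall grade.** "The overall rating is simply the poorest functional status indicated by the patient's answers". Where two grades seem to fit, the instructions assign the higher one.

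Protocol Section 3 lists the PCFS score at discharge and Day 30 as a Phase 3 exploratory endpoint and includes functional outcomes among the Phase 2b exploratory endpoints. SAP Section 7.3.3 plans descriptive statistics only.

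**The concern.** The grade descriptions treat instrumental activities as one group and assign it to Grade 3. The table splits that group, with two items at 4 and one at 3. Because the overall grade is the worst answer, one yes on chores or travel is enough to record the patient at the severe level, although the protocol's own definition calls that limitation moderate.

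What is at stake is the meaning of the boundary between Grades 3 and 4, which a descriptive PCFS table would show directly. A reader who interprets the reported Grade 4 percentage from the grade definition would take it to mean dependence in basic self-care. Under the table it also includes patients who are independent in self-care but need help with daily chores or getting around locally. A rater who worked from the descriptions and one who worked from the table could also grade the same patient differently.

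**Working it through.** No sample size, power or alpha figure is involved. The check sets the two parts of Section 10.4 side by side and applies the worst-answer rule.

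**Step 1: grade by grade text and by table**

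| Item | Subject | Grade text | Table | Agree? |
|---|---|---|---|---|
| 2.1 | Constant care | not named; more dependent than Grade 3 | 4 | no conflict |
| 3.1 | Eating | a basic activity, so 4 | 4 | yes |
| 3.2 | Toilet | 4 (named) | 4 | yes |
| 3.3 | Daily hygiene | 4 (named) | 4 | yes |
| 3.4 | Walking | 4 (functional mobility) | 4 | yes |
| 4.1 | Household chores | 3 (named) | 4 | **no** |
| 4.2 | Local travel | 3 (community mobility) | 4 | **no** |
| 4.3 | Local shopping | 3 (named) | 3 | yes |

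Chores and shopping are matched by name. Local travel is matched to community mobility by meaning, since the wording differs. The match is reasonable because walking around the house or ward is already item 3.4, which leaves item 4.2 to cover movement outside the home.

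**Step 2: apply the rule.** Overall grade for a survivor = maximum of the grades attached to the yes answers.

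| Pattern of yes answers | By table | By grade text | Difference |
|---|---|---|---|
| 4.1 and/or 4.2 only | 4 | 3 | 1 |
| 4.1 and/or 4.2, plus any items graded 3 or lower | max(4, ≤3) = 4 | max(3, ≤3) = 3 | 1 |
| 4.3 only | 3 | 3 | 0 |
| 4.1 and/or 4.2, plus any of 2.1, 3.1 to 3.4 | 4 | 4 | 0 |

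The conflict therefore changes the recorded grade only for patients with a yes on 4.1 or 4.2 and a no on 2.1 and on all of 3.1 to 3.4. For them the shift is exactly one grade. The documents give no figure for how common this pattern is.

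**Step 3: does another rule in Section 10.4 remove the conflict?** The instruction to take the higher grade when two seem to fit does not. It sends these patients to 4 and leaves the Grade 3 description wrong for them.

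**The case against.** The strongest defence is that the table sets a stricter threshold than the text. The Grade 3 description says patients may need assistance, while the table asks whether assistance is essential. Item 4.1 is confined to chores that must be done every day, and under item 4.2 being able to call and direct a taxi counts as independent. The Grade 4 description also speaks of essential help, and its list of activities is only illustrative. On that reading, essential help with daily chores could belong in Grade 4. This does not explain the split, because item 4.3 asks the same question about essential help, under the same shared definition, and is graded 3.

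A second defence stands in part. Raters who follow the table will score consistently, because each answer has a printed grade and the worst one decides. The table is reproducible; the problem is that its result disagrees with the printed definition of the grade.

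A third defence stands in full. The PCFS is a cited external instrument that is not part of these documents, and the scale figure in Section 8.2 is not available here. A reader might infer that patients are over-graded and that the table is simply wrong. The documents do not support that: the table may reproduce the source and the description may be the faulty part. Over-grading holds only relative to the protocol's own Grade 3 text.

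**Conclusion.** The contradiction is real and sits in current protocol text. Its size is one grade, from 3 to 4, for patients who need help with chores or local travel but not with basic activities or constant care. It blurs the moderate/severe boundary. The conclusion assumes that local travel and community mobility mean the same thing; for chores no such assumption is needed.

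Three further inferences may tempt a reader but do not hold:

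- **Grades 3 and 4 can no longer be told apart.** Items 4.3, 5.1, 5.3 and 5.4 still give Grade 3, and items 2.1 and 3.1 to 3.4 give Grade 4 under either version.
- **A stated share of patients is misgraded.** Neither the frequency of the affected answer pattern nor the number of patients assessed at discharge is given, so any count would be a guess.
- **The comparison of rNAPc2 with heparin is biased.** The same table applies in every arm. PCFS is exploratory and descriptive, so no primary endpoint, power or alpha is touched.

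This is a minor point, worth correcting because the correction is cheap.

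**What to change.** 1. Compare the grade descriptions and the interview table in Protocol Section 10.4 with the source instrument that the protocol cites.
2. Unless the source supports grade 4, change items 4.1 and 4.2 to 3, in line with the Grade 3 text and item 4.3. If the source does support 4, leave the table alone and correct the Grade 3 text.
3. Bring the eCRF scoring instructions into line, and state in SAP Section 7.3.3 which scoring version the summaries use.
4. If the table changes, rescore data already collected only if the item-level answers were stored. The documents mention only a PCFS score, so the sponsor has to confirm this. If only overall grades were kept, say in the report which version produced them.

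The cost is two table cells or one passage of descriptive text, a check of the eCRF instructions, and one sentence in the SAP. No change to the design, sample size or testing plan follows.
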